4.4.3 Derived Other Variables

4.4.3.1 Age for Demographics

The age of a subject in the study was the calendar age in days at the time of inclusion.

4.4.3.2 Race, Preterm and Full-term Birth for Subgroup Analysis

Race will be presented as a demographic characteristic of interest using the following modalities:

- White
- Black
- Asian
- Other

Note: The original race categories collected in the study will still be used for demographics analyses. The American Indian or Alaska Native, Native Hawaiian or Other Pacific Islander, Mixed origin, Not Reported and Unknown will be classified to “Other” stratum for subgroup analysis purpose only.

Preterm will be derived as gestational age less than 37 weeks, and full-term birth will be defined as gestational age having at least 37 weeks between Group 1 and Group 2.

4.4.3.3 Subject Duration

The duration of a subject in the study until last visit is computed as follows:

Maximum (Date of last visit, Date of term form) – (Date of V01) +1.

The duration of a subject in the study including follow-up is computed as follows:

Maximum (Date of last visit, Date of term form, Date of last follow-up contact) – (Date of V01) +1.

4.4.3.4 Duration of the Study

The duration of the study until last visit is computed as follows:

Maximum of all subjects (Date of last visit, Date of termination form) – minimum for all subjects (Date of V01) +1.

The duration of the study including follow-up is computed as follows:

Maximum of all subjects (Date of last visit, Date of termination form, Date of last follow-up contact) – minimum for all subjects (Date of V01) +1

5 Statistical Methods and Determination of Sample Size

The statistical analyses will be performed under the responsibility of the Sponsor's Biostatistics platform using SAS® Version 9.4 software or later. The results of the statistical analysis will be available in the final clinical study report (CSR).

For descriptive purposes, the following statistics in [Table 5.1](#) will be presented. In general, categorical variables will be summarized and presented by frequency counts, proportion percentages and confidence interval CIs. The 95% CIs of point estimates will be calculated using the normal approximation for quantitative data and the exact binomial distribution (Clopper-Pearson method) for proportions ([14](#)).

For immunogenicity results, assuming that Log_{10} transformation of the titers / data follows a normal distribution, at first, the mean and the 95% CI will be calculated on Log_{10} (titers / data) using the usual calculation for normal distribution (using Student's t distribution with $n-1$ degree of freedom), then antilog transformations will be applied to the results of calculations, in order to provide geometric means (GMs) and their 95% CI. For GMTs and GMCs, 95% CIs of point estimates will be calculated using normal approximation assuming they are log-normally distributed (log_{10} scale).

Reverse cumulative distribution curve (RCDC) figures will be provided for the antibody titers against meningococcal serogroups A, C, W, and Y.

Table 5.1: Descriptive statistics produced

Baseline characteristics and follow-up description	Categorical data	Number of subjects. Percentage of subjects.
	Continuous data	Mean, standard deviation, quartiles, minimum, and maximum.
Clinical safety results	Categorical data	Solicited: Number and percentage (95% CIs) of subjects. Unsolicited: Number and percentage (95% CIs) of subjects, and number of events.
Immunogenicity results	Categorical data (seroresponse, vaccine response, cutoff)	Number and percentage (95% CIs) of subjects.
	Continuous data (titer / concentration)	Log ₁₀ : Mean and standard deviation. Anti-Log ₁₀ (work on Log ₁₀ distribution, and anti-Log ₁₀ applied): Geometric mean (GM), 95% CI of the GM Graphical representation by Reverse Cumulative Distribution Curve (RCDC).

5.1 Statistical Methods

5.1.1 Hypotheses and Statistical Methods for Primary Objectives

5.1.1.1 Hypotheses

The primary objectives will be met if the following primary hypotheses are rejected:

- **Primary Hypothesis 1 (MenACYW vaccine seroresponse rate after 4th dose):**

Thirty days after the administration of the 4th dose of MenACYW conjugate vaccine at 12 to 15 months of age or MENVEO at 12 months of age, the percentages of subjects who achieve an hSBA seroresponse for meningococcal serogroups A, C, Y, and W in Subgroup 1a are non-inferior to the corresponding percentages in Subgroup 2a.

Null hypothesis (H0): $p(\text{men, G1a}) - p(\text{men, G2a}) \leq - 10\%$

Alternative hypothesis (H1): $p(\text{men, G1a}) - p(\text{men, G2a}) > - 10\%$

where $p(\text{men, G1a})$ and $p(\text{men, G2a})$ are the percentages of subjects who achieve hSBA vaccine seroresponse^a in Subgroup 1a and Subgroup 2a, respectively. Each of the serogroups A, C, Y, and W will be tested separately. If the lower limit of the 2-sided 95% confidence interval (CI) of the difference between the 2 proportions is $> - 10\%$ for each serogroup, the inferiority assumption will be rejected.

^a hSBA vaccine seroresponse for serogroups A, C, Y and W is defined as:

- For a subject with a pre-vaccination titer $< 1:8$, the post-vaccination titer must be $\geq 1:16$.
- For a subject with a pre-vaccination titer $\geq 1:8$, the post-vaccination titer must be at least 4-fold greater than the pre-vaccination titer.

The overall non-inferiority of this primary hypothesis 1 will be demonstrated if all 4 individual null hypotheses are rejected.

- **Primary Hypothesis 2 (MenACYW hSBA titer $\geq 1:8$ after 3rd dose)**

Thirty days after the administration of the 3rd dose of MenACYW conjugate vaccine or MENVEO at 6 months of age, the percentages of subjects who achieve hSBA $\geq 1:8$ for meningococcal serogroups A, C, Y, and W in Group 1 are non-inferior to the corresponding percentages in Group 2.

Null hypothesis (H0): $p(\text{men, G1}) - p(\text{men, G2}) \leq -10\%$

Alternative hypothesis (H1): $p(\text{men, G1}) - p(\text{men, G2}) > -10\%$

where $p(\text{men, G1})$ and $p(\text{men, G2})$ are the percentages of subjects who achieve hSBA achieve $\geq 1:8$ in Group 1 and Group 2, respectively. Each of the serogroups A, C, Y, and W will be tested separately. If the lower limit of the 2-sided 95% CI of the difference between the 2 proportions is $> -10\%$ for each serogroup, the inferiority assumption will be rejected.

The overall non-inferiority of this primary hypothesis 2 will be demonstrated if all 4 individual null hypotheses are rejected.

5.1.1.2 Statistical Methods

For these two primary hypotheses, each of the serogroups A, C, Y, and W will be tested separately. If the lower limit of the 2-sided 95% confidence interval (CI) of the difference between the 2 proportions is $> -10\%$ for each serogroup, the inferiority assumption will be rejected.

For each of the 4 non-inferiority hypotheses using the percentage rates (eg, the percentage of subjects achieving hSBA vaccine seroresponse rates or hSBA $\geq 1:8$), the CI of the difference in proportions will be computed using the Wilson Score method without continuity correction (15).

Let $\hat{\theta} = p_1 - p_2$, then $L = \hat{\theta} - \delta$ and $U = \hat{\theta} + \varepsilon$ are respectively the lower and the upper limits of the CI, where:

$$\delta = Z_{0.025} \sqrt{\left\{ \frac{l_1(1-l_1)}{n_1} + \frac{u_2(1-u_2)}{n_2} \right\}}$$
$$\varepsilon = Z_{0.025} \sqrt{\left\{ \frac{l_2(1-l_2)}{n_2} + \frac{u_1(1-u_1)}{n_1} \right\}}$$

l_1 and u_1 are calculated from the CI of the single proportion in Group I given by:

$$\frac{(2n_1p_1 + Z_{0.025}^2 \pm Z_{0.025} \sqrt{(Z_{0.025}^2 + 4n_1p_1(1-p_1))}}{2(n_1 + Z_{0.025}^2)}$$

l_2 and u_2 are calculated from the CI of the single proportion in Group II given by:

$$\frac{(2n_2p_2 + Z_{0.025}^2 \pm Z_{0.025} \sqrt{(Z_{0.025}^2 + 4n_2p_2(1-p_2))}}{2(n_2 + Z_{0.025}^2)}$$

where $Z_{0.025}$ is the upper 97.5th percentile of the standard normal distribution.

For primary hypothesis 1, where Group I and Group II above refer to Subgroup 1a and 2a, respectively. For primary hypothesis 2, where Group I and Group II above refer to Group 1 and Group 2, respectively.

5.1.2 Hypotheses and Statistical Methods for Secondary Objectives

Summary of non-inferiority hypotheses for the secondary objectives are described in [Table 5.2](#).

5.1.2.1 Hypotheses

I. First year evaluation at 30 days after the 6-month vaccinations (after the 3rd dose)

- **Secondary Hypothesis 1 (Anti-hepatitis B % \geq 10 mIU/mL)**

Thirty days after the 6-month HB vaccine administration, the percentage of subjects who achieve ≥ 10 mIU/mL in anti-HB surface antibody concentrations in Group 1 is non-inferior to that in Group 2.

Null hypothesis (H0): $p(\text{hep, G1}) - p(\text{hep, G2}) \leq - 10\%$

Alternative hypothesis (H1): $p(\text{hep, G1}) - p(\text{hep, G2}) > - 10\%$

where $p(\text{hep, G1})$ and $p(\text{hep, G2})$ are the percentages of subjects in Group 1 and Group 2, respectively, who achieve ≥ 10 mIU/mL in anti-HB surface antibody concentrations. If the lower limit of the 2-sided 95% CI of the difference between the 2 proportions is $> - 10\%$, the inferiority assumption will be rejected.

- **Secondary Hypothesis 2 (Anti-PRP % ≥ 0.15 $\mu\text{g/mL}$)**

Thirty days after the 6-month Pentacel® vaccination, the percentage of subjects who achieve ≥ 0.15 $\mu\text{g/mL}$ in anti-PRP antibody concentrations in Group 1 are non-inferior to that in Group 2.

Null hypothesis (H0): $p(\text{prp, G1}) - p(\text{prp, G2}) \leq - 5\%$

Alternative hypothesis (H1): $p(\text{prp, G1}) - p(\text{prp, G2}) > - 5\%$

where $p(\text{prp, G1})$ and $p(\text{prp, G2})$ are the percentages of subjects in Group 1 and Group 2, respectively, who achieve ≥ 0.15 $\mu\text{g/mL}$ in anti-PRP antibody concentrations. If the lower limit of the 2-sided 95% CI of the difference between the 2 proportions is $> - 5\%$, the inferiority assumption will be rejected.

- **Secondary Hypothesis 3 (Anti-PRP % ≥ 1.0 $\mu\text{g/mL}$)**

Thirty days after the 6-month Pentacel® vaccination, the percentage of subjects who achieve ≥ 1.0 $\mu\text{g/mL}$ in anti-PRP antibody concentrations in Group 1 are non-inferior to that in Group 2.

Null hypothesis (H0): $p(\text{prp, G1}) - p(\text{prp, G2}) \leq - 10\%$

Alternative hypothesis (H1): $p(\text{prp, G1}) - p(\text{prp, G2}) > - 10\%$

where $p(\text{prp, G1})$ and $p(\text{prp, G2})$ are the percentage of subjects in Group 1 and Group 2, respectively, who achieve ≥ 1.0 $\mu\text{g/mL}$ in anti-PRP antibody concentrations. If the lower limit of the 2-sided 95% CI of the difference between the 2 proportions is $> - 10\%$, the inferiority assumption will be rejected.

- **Secondary Hypothesis 4 (Anti-polio % titer $\geq 1:8$)**

Thirty days after the 6-month Pentacel® vaccination, the percentages of subjects who achieve $\geq 1:8$ in anti-polio antibody titers (type 1, type 2, and type 3) in Group 1 are non-inferior to those in Group 2.

Null hypothesis (H0): $p(\text{pol, G1}) - p(\text{pol, G2}) \leq - 5\%$

Alternative hypothesis (H1): $p(\text{pol, G1}) - p(\text{pol, G2}) > -5\%$
where $p(\text{pol, G1})$ and $p(\text{pol, G2})$ are the percentages of subjects in Group 1 and Group 2, respectively, who achieve $\geq 1:8$ in anti-polio antibody titers (type 1, type 2, and type 3). Each of the antigens of type 1, type 2, and type 3 will be tested separately. If the lower limit of the 2-sided 95% CI of the difference between the 2 proportions is $> -5\%$ for each type, the inferiority assumption will be rejected.

- **Secondary Hypothesis 5 (Anti- rotavirus % \geq 3-fold rise)**

Thirty days after the 6-month rotavirus vaccine administration, the percentages of subjects who achieve ≥ 3 -fold rise in serum IgA antibody concentrations against the rotavirus in Group 1 is non-inferior to those in Group 2.

Null hypothesis (H0): $p(\text{rota, G1}) - p(\text{rota, G2}) \leq -10\%$

Alternative hypothesis (H1): $p(\text{rota, G1}) - p(\text{rota, G2}) > -10\%$
where $p(\text{rota, G1})$ and $p(\text{rota, G2})$ are the percentages of subjects in Group 1 and Group 2, respectively, who achieve ≥ 3 -fold rise in serum anti-rotavirus IgA antibody concentrations (serotypes G1, G2, G3, G4, and P1A[8]). If the lower limit of the 2-sided 95% CI of the difference between the 2 proportions is $> -10\%$, the inferiority assumption will be rejected.

- **Secondary Hypothesis 6 (Anti-rotavirus; GMC)**

Thirty days after the 6-month rotavirus vaccine administration, the GMCs of the serum IgA antibodies against the rotavirus in Group 1 are non-inferior to the GMCs in Group 2.

Null hypothesis (H0): $\text{GMC}(\text{rota, G1}) / \text{GMC}(\text{rota, G2}) \leq 2/3$

Alternative hypothesis (H1): $\text{GMC}(\text{rota, G1}) / \text{GMC}(\text{rota, G2}) > 2/3$

where $\text{GMC}(\text{rota, G1})$ and $\text{GMC}(\text{rota, G2})$ are the GMCs of the serum IgA antibodies against the rotavirus in Group 1 and Group 2, respectively. If the lower limit of the 2-sided 95% CI of the ratio of the GMCs from the 2 groups is $> 2/3$, the inferiority assumption will be rejected.

- **Secondary Hypothesis 7 (Anti-pertussis; GMC)**

Thirty days after the 6-month Pentacel® vaccination, the GMCs of antibodies against the pertussis antigens (PT, FHA, PRN, and FIM) in Group 1 are non-inferior to the GMCs in Group 2.

Null hypothesis (H0): $\text{GMC}(\text{pert, G1}) / \text{GMC}(\text{pert, G2}) \leq 2/3$

Alternative hypothesis (H1): $\text{GMC}(\text{pert, G1}) / \text{GMC}(\text{pert, G2}) > 2/3$

where $\text{GMC}(\text{pert, G1})$ and $\text{GMC}(\text{pert, G2})$ are the GMCs of antibodies against the pertussis antigens (PT, FHA, PRN, and FIM) in Group 1 and Group 2, respectively.

Each of the antigens of PT, FHA, PRN, and FIM will be tested separately. If the lower limit of the 2-sided 95% CI of the ratio of the GMCs from the 2 groups is $> 2/3$ for each antigen, the inferiority assumption will be rejected.

- **Secondary Hypothesis 8 (Anti-pneumococcal; GMC)**

Thirty days after the 6-month Prevnar 13® vaccination, the GMCs of antibodies against the pneumococcal antigens (serotypes 1, 3, 4, 5, 6A, 6B, 7F, 9V, 14, 18C, 19A, 19F, and 23F) in Group 1 are non-inferior to the GMCs in Group 2.

Null hypothesis (H0): $\text{GMC}(\text{pne, G1}) / \text{GMC}(\text{pne, G2}) \leq 1/2$

Alternative hypothesis (H1): $\text{GMC}(\text{pne, G1}) / \text{GMC}(\text{pne, G2}) > 1/2$

where $\text{GMC}(\text{pne, G1})$ and $\text{GMC}(\text{pne, G2})$ are the GMCs of antibodies against the pneumococcal antigens (serotypes 1, 3, 4, 5, 6A, 6B, 7F, 9V, 14, 18C, 19A, 19F, and 23F) in Group 1 and Group 2, respectively.

Each of the serotypes 1, 3, 4, 5, 6A, 6B, 7F, 9V, 14, 18C, 19A, 19F, and 23F will be tested separately. If the lower limit of the 2-sided 95% CI of the ratio of the GMCs from the 2 groups is $> 1/2$ for each serotype, the inferiority assumption will be rejected.

II. Second year evaluation at 30 days after the 12-month vaccinations

- **Secondary Hypothesis 9 (Anti- measles % \geq 255 mIU/mL)**

Thirty days after the 12-month M-M-R® II vaccination, the percentages of subjects who achieve \geq 255 mIU/mL in anti-measles antibody concentrations in Subgroup 1a are non-inferior to those in Subgroup 2a.

Null hypothesis (H0): $p(\text{mea, G1a}) - p(\text{mea, G2a}) \leq - 10\%$

Alternative hypothesis (H1): $p(\text{mea, G1a}) - p(\text{mea, G2a}) > - 10\%$

where $p(\text{mea, G1a})$ and $p(\text{mea, G2a})$ are the percentages of subjects in Subgroup 1a and Subgroup 2a, respectively, who achieve \geq 255 mIU/mL in anti-measles antibody concentrations. If the lower limit of the 2-sided 95% CI of the difference between the 2 proportions is $> - 10\%$, the inferiority assumption will be rejected.

- **Secondary Hypothesis 10 (Anti-mumps% \geq 10 mumps Ab units/mL)**

Thirty days after the 12-month M-M-R® II vaccination, the percentages of subjects who achieve \geq 10 Mumps Ab units/mL in anti-mumps antibody concentrations in Subgroup 1a are non-inferior to those in Subgroup 2a.

Null hypothesis (H0): $p(\text{mum, G1a}) - p(\text{mum, G2a}) \leq - 10\%$

Alternative hypothesis (H1): $p(\text{mum, G1a}) - p(\text{mum, G2a}) > - 10\%$

where $p(\text{mum, G1a})$ and $p(\text{mum, G2a})$ are the percentages of subjects in Subgroup 1a and Subgroup 2a, respectively, who achieve \geq 10 Mumps Ab units/mL in anti-mumps antibody concentrations. If the lower limit of the 2-sided 95% CI of the difference between the 2 proportions is $> - 10\%$, the inferiority assumption will be rejected.

- **Secondary Hypothesis 11 (Anti-rubella% \geq 10 IU/mL)**

Thirty days after the 12-month M-M-R® II vaccination, the percentages of subjects who achieve \geq 10 IU/mL in anti-rubella antibody concentrations in Subgroup 1a are non-inferior to those in Subgroup 2a.

Null hypothesis (H0): $p(\text{rub, G1a}) - p(\text{rub, G2a}) \leq - 10\%$

Alternative hypothesis (H1): $p(\text{rub, G1a}) - p(\text{rub, G2a}) > - 10\%$

where $p(\text{rub, G1a})$ and $p(\text{rub, G2a})$ are the percentage of subjects in Subgroup 1a and Subgroup 2a, respectively, who achieve \geq 10 IU/mL in anti-rubella antibody concentrations. If the lower limit of the 2-sided 95% CI of the difference between the 2 proportions is $> - 10\%$, the inferiority assumption will be rejected.

- **Secondary Hypothesis 12 (Anti-varicella% \geq 5 gpELISA Ab units/mL)**

Thirty days after the 12-month VARIVAX® vaccination, the percentage of subjects who achieve \geq 5 gpELISA units/mL in anti-varicella antibody concentrations in Subgroup 1a is non-inferior to those in Subgroup 2a.

Null hypothesis (H0): $p(\text{var, G1a}) - p(\text{var, G2a}) \leq - 10\%$

Alternative hypothesis (H1): $p(\text{var, G1a}) - p(\text{var, G2a}) > - 10\%$

where $p(\text{var, G1a})$ and $p(\text{var, G2a})$ are the percentages of subjects in Subgroup 1a and Subgroup 2a, respectively, who achieve \geq 5 gpELISA units/mL in anti-varicella antibody concentrations. If the lower limit of the 2-sided 95% CI of the difference between the 2 proportions is $> - 10\%$, the inferiority assumption will be rejected.

- **Secondary Hypothesis 13 (Anti-pneumococcal; GMC)**

Thirty days after the 12-month Prevnar13® vaccination, the GMCs of antibodies against the pneumococcal antigens (serotypes 1, 3, 4, 5, 6A, 6B, 7F, 9V, 14, 18C, 19A, 19F, and 23F) in Subgroup 1a are non-inferior to the GMCs in Subgroup 2a.

Null hypothesis (H0): $\text{GMC}(\text{pne, G1a}) / \text{GMC}(\text{pne, G2a}) \leq 1/2$

Alternative hypothesis (H1): $\text{GMC}(\text{pne, G1a}) / \text{GMC}(\text{pne, G2a}) > 1/2$

where $\text{GMC}(\text{pne, G1a})$ and $\text{GMC}(\text{pne, G2a})$ are the GMCs of antibodies against the pneumococcal antigens (serotypes 1, 3, 4, 5, 6A, 6B, 7F, 9V, 14, 18C, 19A, 19F, and 23F) in Subgroup 1a and Subgroup 2a, respectively. Each of the serotypes 1, 3, 4, 5, 6A, 6B, 7F, 9V, 14, 18C, 19A, 19F, and 23F will be tested separately. If the lower limit of the 2-sided 95% CI of the ratio of the GMCs from the 2 groups is $> 1/2$ for each serotype, the inferiority assumption will be rejected.

III. Second year evaluation at 30 days after the 15-month vaccination

- **Secondary Hypothesis 14 (Anti-PRP% $\geq 1.0 \mu\text{g/mL}$)**

Thirty days after the 15-month Pentacel® vaccination, the percentage of subjects who achieve $\geq 1.0 \mu\text{g/mL}$ in anti-PRP antibody concentrations in Subgroup 1b is non-inferior to that in Subgroup 2b.

Null hypothesis (H0): $p(\text{prp, G2b}) - p(\text{prp, G1b}) \leq -10\%$

Alternative hypothesis (H1): $p(\text{prp, G2b}) - p(\text{prp, G1b}) > -10\%$

where $p(\text{prp, G1b})$ and $p(\text{prp, G2b})$ are the percentages of subjects in Subgroup 1b and Subgroup 2b, respectively, who achieve $\geq 1.0 \mu\text{g/mL}$ in anti-PRP antibody concentrations. If the lower limit of the 2-sided 95% CI of the difference between the 2 proportions is $> -10\%$, the inferiority assumption will be rejected.

- **Secondary Hypothesis 15 (Anti-polio % titer ≥ 8)**

Thirty days after the 15-month Pentacel® vaccination, the percentages of subjects who achieve $\geq 1:8$ in anti-polio antibody titers (type 1, type 2, and type 3) in Subgroup 1b are non-inferior to those in Subgroup 2b.

Null hypothesis (H0): $p(\text{pol, G1b}) - p(\text{pol, G2b}) \leq -5\%$

Alternative hypothesis (H1): $p(\text{pol, G1b}) - p(\text{pol, G2b}) > -5\%$

where $p(\text{pol, G1b})$ and $p(\text{pol, G2b})$ are the percentages of subjects in Subgroup 1b and Subgroup 2b, respectively, who achieve $\geq 1:8$ in anti-polio antibody titers (type 1, type 2, and type 3). Each of the antigens of type 1, type 2, and type 3 will be tested separately. If the lower limit of the 2-sided 95% CI of the difference between the 2 proportions is $> -5\%$ for each serotype, the inferiority assumption will be rejected.

- **Secondary Hypothesis 16 (Anti-pertussis; vaccine response rate)**

Thirty days after the 15-month Pentacel® vaccination, the percentages of subjects with a pertussis vaccine response^a for the pertussis antigens (PT, FHA, PRN, and FIM) in Subgroup 1b are non-inferior to the percentages in Subgroup 2b.

Null hypothesis (H0): $p(\text{pert, G1b}) - p(\text{pert, G2b}) \leq -10\%$

Alternative hypothesis (H1): $p(\text{pert, G1b}) - p(\text{pert, G2b}) > -10\%$

^a Pertussis vaccine response is defined as:

- Pre-booster (4th) vaccination concentration $<$ LLOQ, then post-booster (4th) vaccination concentration should be ≥ 4 times the LLOQ
- Pre-booster (4th) vaccination concentration \geq LLOQ but $<$ 4 times the LLOQ, then post-booster (4th) vaccination concentration should achieve a 4-fold rise (post-4th vaccination/ Pre-4th vaccination ≥ 4)
- Pre-booster (4th) vaccination concentration \geq 4 times the LLOQ, then post-booster (4th) vaccination concentration should achieve a 2-fold response (post-4th vaccination/ Pre-4th vaccination ≥ 2)

where $p(\text{pert, G1b})$ and $p(\text{pert, G2b})$ are the percentages of subjects who achieve a pertussis vaccine response^a in Subgroup 1b and Subgroup 2b, respectively. Each of the antigens of PT, FHA, PRN, and FIM will be tested separately. If the lower limit of the 2-sided 95% CI of the difference between the 2 proportions is $> -10\%$ for each antigen, the inferiority assumption will be rejected.

Table 5.2: Summary of non-inferiority hypotheses for the secondary objectives

Evaluation Time	Comparison Groups (G)	Antigen	Endpoint	Non-inferiority margin	Hypothesis #
1st Year, 30 days after the 6-month vaccination	G1 vs G2	Hepatitis B	% ≥ 10 mIU/mL	10%	1
		PRP	% ≥ 0.15 $\mu\text{g}/\text{mL}$	5%	2
		PRP	% ≥ 1.0 $\mu\text{g}/\text{mL}$	10%	3
		Polio [†]	% $\geq 1:8$	5%	4
		Rotavirus	% \geq 3-fold rise	10%	5
		Rotavirus	GMC	1.5	6
		Pertussis*	GMC	1.5	7
		Pneumococcal [‡]	GMC	2	8
2nd Year, 30 days after the 12-month vaccination	G1a vs G2a	Measles	% ≥ 255 mIU/mL	10%	9
		Mumps	% ≥ 10 mumps Ab units/mL	10%	10
		Rubella	% ≥ 10 IU/mL	10%	11
		Varicella	% ≥ 5 gpELISA units/mL	10%	12
		Pneumococcal [‡]	GMC	2	13
2nd Year, 30 days after the 15-month vaccination	G1b vs G2b	PRP	% $\geq 1.0\mu\text{g}/\text{mL}$	10%	14
		Polio [†]	% $\geq 1:8$	5%	15
		Pertussis*	Response rate	10%	16

* Pertussis: PT, FHA, PRN, and FIM

† Polio: type 1, type 2, type 3

‡ Pneumococcal: 1, 3, 4, 5, 6A, 6B, 7F, 9V, 14, 18C, 19A, 19F, and 23F

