5.1.2.2 Statistical Methods

- For each of the non-inferiority hypotheses (hypothesis 1 to 5, 9 to 12 and 14 to 16) using the percentage rates (eg, vaccine response rate), the CI of the difference in proportions will be computed using the Wilson Score method without continuity correction (15).

Let $\hat{\theta} = p_1 - p_2$, then $L = \hat{\theta} - \delta$ and $U = \hat{\theta} + \varepsilon$ are respectively the lower and the upper limits of the CI, where:

$$\delta = Z_{0.025} \sqrt{\left\{ \frac{l_1(1-l_1)}{n_1} + \frac{u_2(1-u_2)}{n_2} \right\}}$$

$$\varepsilon = Z_{0.025} \sqrt{\left\{ \frac{l_2(1-l_2)}{n_2} + \frac{u_1(1-u_1)}{n_1} \right\}}$$

l_1 and u_1 are calculated from the CI of the single proportion in Group I given by:

$$\frac{(2n_1p_1 + Z_{0.025}^2 \pm Z_{0.025} \sqrt{(Z_{0.025}^2 + 4n_1p_1(1-p_1))})}{2(n_1 + Z_{0.025}^2)}$$

l_2 and u_2 are calculated from the CI of the single proportion in Group II given by:

$$\frac{(2n_2p_2 + Z_{0.025}^2 \pm Z_{0.025} \sqrt{(Z_{0.025}^2 + 4n_2p_2(1-p_2))})}{2(n_2 + Z_{0.025}^2)}$$

where $Z_{0.025}$ is the upper 97.5th percentile of the standard normal distribution.

where Group I and Group II above refer to Group 1a and Group 2a, Subgroup 1 and 2, or Subgroup 1b and 2b respectively for corresponding hypotheses.

- For each of the non-inferiority hypotheses (hypothesis 6 to 8 and 13) using the GMC ratios, the statistical methodology will be based on the use of the 2-sided 95% CI of difference in means of post-vaccination Log10 transformed concentrations between Group 1 and Group 2 or between Subgroup 1a and Subgroup 2a with normal approximation. Logarithm transformation of the individual post-vaccination concentrations will be calculated. Assuming that Log₁₀ transformation of the data is normally distributed, the 95% CI for the difference in Log₁₀(GMC) between two groups will be in the form:

$$\bar{X}_i - \bar{X}_j \pm t(1 - \alpha/2, n_i + n_j - 2) \cdot S \sqrt{1/n_i + 1/n_j}$$

where $\bar{X}_i = \log_{10}(\text{GMC})$ is the mean of $\log_{10}(\text{concentration})$ of Group i ,

$S^2 = [(n_i - 1) S_i^2 + (n_j - 1) S_j^2] / (n_i + n_j - 2)$ is the pooled sample variance,

n_i and S_i^2 are the sample size and sample variance of Group i ,

$t(1 - \alpha/2, n_i + n_j - 2)$ is the 100(1- $\alpha/2$) percentile of the t -distribution with degrees of freedom $df = n_i + n_j - 2$.

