13	Pneumococcal 1	GMC	2	4.0 (2.2,7.2) SD= 1.37	> 99.9
	Pneumococcal 3	GMC	2	2.1 (1.5, 3.1) SD= 0.86	> 99.9
	Pneumococcal 4	GMC	2	2.2 (1.5,3.2) SD= 0.87	> 99.9
	Pneumococcal 5	GMC	2	1.3 (0.9, 2.0) SD= 1.00	> 99.9
	Pneumococcal 6A	GMC	2	10.4 (6.3,17.3) SD= 1.18	> 99.9
	Pneumococcal 6B	GMC	2	7.7 (4.5,13.4) SD= 1.29	> 99.9
	Pneumococcal 7F	GMC	2	7.0 (4.4, 11.0) SD= 1.05	> 99.9
	Pneumococcal 9V	GMC	2	1.9 (1.5, 2.5) SD= 0.64	> 99.9
	Pneumococcal 14	GMC	2	10.0 (4.9, 20.2) SD= 1.64	> 99.9
	Pneumococcal 18C	GMC	2	2.9 (2.2, 3.9) SD= 0.69	> 99.9
	Pneumococcal 19A	GMC	2	9.1 (5.4, 15.1)	> 99.9

Hypothesis #	Antigen	Endpoint	Non-inferiority margin	Estimated response*	Power (%)
				SD=1.12	
	Pneumococcal 19F	GMC	2	14.0 (9.3, 21.0) SD=0.94	> 99.9
	Pneumococcal 23F	GMC	2	8.6 (5.7, 13.2) SD=1.00	> 99.9
	Overall				> 99.9

Evaluable subjects: of Subgroup 1a : n=770 subjects; Subgroup 2a: n = 385 subjects

*All estimates are from MET39, Group 1, 13-month data, except for the measles, mumps, rubella, and varicella estimates from study V59P21 (NCT00626327) and study V419-007 (NCT01341639).

III. Second year evaluation at 30 days after the 15-month vaccinations

With 385 evaluable subjects in Subgroup 1b and 192 evaluable subjects in Subgroup 2b, the study will have around 98.6% power by using the Farrington and Manning's method to declare the non-inferiority of Subgroup 1b vs. Subgroup 2b.

Table 5.9: Power estimates to reject the secondary hypotheses 14, 15, and 16

Hypothesis #	Antigen	Endpoints	Non-inferiority margin	Estimated response*	Power (%)
14	PRP	% \geq 1.0 μ g/mL	10%	95%	99.9
15	Polio type 1	% \geq 1:8	5%	\geq 99%	99.8
	Polio type 2	% \geq 1:8	5%	\geq 99%	99.9
	Polio type 3	% \geq 1:8	5%	\geq 99%	99.9
16	PT	Response Rate	10%	94%	99.8
	FHA	Response Rate	10%	95%	99.9
	PRN	Response Rate	10%	93%	99.5
	FIM	Response Rate	10%	95%	99.9
	Overall				98.6

Evaluable subjects: Subgroup 1b: n=385 subjects; Subgroup 2b: n = 192 subjects

*All estimates are from MET39, Group 2, 16-month data

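### Secondary Hypothesis 14 prints its null and alternative the wrong way round (2b minus 1b), against its own stated aim and the SAP's interval definition

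*SAP*

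**What the plan says.** SAP 5.1.2.1, part III, opens Secondary Hypothesis 14 with the aim that the percentage reaching at least 1.0 µg/mL "in anti-PRP antibody concentrations in Subgroup 1b is non-inferior to that in Subgroup 2b". The null that follows is "p(\text{prp, G2b}) - p(\text{prp, G1b}) \leq -10"% and the alternative is "p(\text{prp, G2b}) - p(\text{prp, G1b}) > -10"%. The decision sentence compares the lower limit of the two-sided 95% interval with -10% but does not say which group is subtracted from which. The protocol synopsis and protocol 12.1.2.1 carry the same two reversed lines. SAP 5.8, which lists changes to the planned analyses, does not mention them.

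Hypothesis 16 concerns the same subgroups at the same visit, and its null is "p(\text{pert, G1b}) - p(\text{pert, G2b}) \leq -10"%. SAP 5.1.2.2 gives the interval method "For each of the non-inferiority hypotheses (hypothesis 1 to 5, 9 to 12 and 14 to 16) using the percentage rates". It defines the estimate as p1 - p2, "where Group I and Group II above refer to Group 1a and Group 2a, Subgroup 1 and 2, or Subgroup 1b and 2b respectively". SAP 5.6 states: "With 385 evaluable subjects in Subgroup 1b and 192 evaluable subjects in Subgroup 2b, the study will have around 98.6% power" for showing non-inferiority of 1b against 2b.

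**The concern.** A non-inferiority null has to name the arm under test first if it is to guard against that arm being worse. With 2b - 1b and a bound of -10%, the null is that MENVEO recipients respond at least 10 points less often than MenACYW recipients. Rejecting it says nothing about whether MenACYW lowers the Hib response.

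Hypothesis 14 is the only formal test of the Hib booster response. At that visit Subgroup 1b receives MenACYW with Pentacel and hepatitis A vaccine, while 2b receives Pentacel and hepatitis A vaccine without a meningococcal vaccine. If the printed null governed, a reduced Hib response in 1b would pass and a better one could fail. The printed hypothesis and the calculation section can therefore give opposite verdicts on the same data.

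**Working it through.** **1. Which direction each place gives**

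| Place | Direction |
|---|---|
| H14 aim sentence (synopsis, protocol 12.1.2.1, SAP 5.1.2.1) | 1b non-inferior to 2b |
| H14 null and alternative (same three places) | 2b - 1b |
| H14 decision sentence | no order named |
| H15 and H16, same subgroups and visit | 1b - 2b |
| H1 to H5 and H9 to H12 | MenACYW group minus MENVEO group |
| Protocol Table 12.1, SAP Table 5.2 | 1b vs 2b |
| SAP 5.1.2.2 | p1 - p2, with 1b as Group I and 2b as Group II |
| SAP 5.6 power text | 1b vs 2b |

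Only the two printed formulae run the other way.

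**2. The stated power for H14 (99.9%)**

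Inputs from SAP 5.6 and Table 5.9: 385 evaluable in 1b, 192 in 2b, 95% response in both, margin 10%, Farrington-Manning method. The two-sided 95% limit gives z = 1.96.

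Power = Φ[(p_test - p_ref + 0.10 - 1.96·SE0) / SE1], where SE0 uses the maximum-likelihood rates restricted to a difference of -10%.

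SE1 = √(0.95·0.05/385 + 0.95·0.05/192) = 0.01926 in either direction.

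- 1b - 2b: restricted rates are 0.8784 (1b) and 0.9784 (2b), so SE0 = 0.01968. (0.10 - 1.96·0.01968)/0.01926 = 3.19, and power is **99.93%**.
- 2b - 1b: restricted rates are 0.8631 (2b) and 0.9631 (1b), so SE0 = 0.02661. (0.10 - 1.96·0.02661)/0.01926 = 2.48, and power is **99.35%**.

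The stated 99.9% fits only 1b - 2b. The overall figure agrees. The eight powers in Table 5.9 multiply to 0.999·0.998·0.999·0.999·0.998·0.999·0.995·0.999 = 0.986, the stated 98.6%. With 0.9935 for H14 the product would be 0.986·0.9935/0.999 = 0.981.

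**3. One data set, two verdicts (illustrative counts)**

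Take 327/385 = 84.9% in 1b and 182/192 = 94.8% in 2b. The single-proportion Wilson limits are 0.8102 to 0.8816 for 1b and 0.9068 to 0.9715 for 2b. The difference 1b - 2b is -0.0986.

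- δ = 1.96·√(0.8102·0.1898/385 + 0.9715·0.0285/192) = 0.0457
- ε = 1.96·√(0.9068·0.0932/192 + 0.8816·0.1184/385) = 0.0523

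The interval for 1b - 2b is -14.4% to -4.6%. Its lower limit is below -10%, so the test fails. For 2b - 1b the interval is 4.6% to 14.4%, and the test passes.

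**4. Probability of passing**

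All binomial outcomes for n = 385 and 192 were enumerated with the SAP 5.1.2.2 limits, counting those with a lower limit above -10%. Only the first row uses rates from the documents; the rest are illustrative.

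| True rate 1b | True rate 2b | Intended (1b - 2b) | Printed (2b - 1b) |
|---|---|---|---|
| 95% | 95% | 0.9999 | 0.9929 |
| 92% | 95% | 0.940 | 0.9997 |
| 90% | 95% | 0.665 | 1.000 |
| 85% | 95% | 0.028 | 1.000 |
| 80% | 95% | 0.0001 | 1.000 |
| 97% | 90% | 1.000 | 0.202 |

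**The case against.** The best defence is that the SAP settles the direction despite the slip. The verdict comes from a confidence interval, and the only place that defines that interval is SAP 5.1.2.2, which names Hypothesis 14 and puts 1b first. The aim sentence, Table 5.2 and the power text agree, and the power figure suggests the sponsor's own calculation ran in the intended direction. At the only response rate the documents give, the two directions reach different verdicts in about 0.7% of trials. The large contrasts need rates that are not in the documents and an analyst who overrides SAP 5.1.2.2.

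Much of this stands. The intended reading is clear, the method itself is not in dispute, and an analyst who follows SAP 5.1.2.2 will compute the right interval. A deficit in 1b would also show in that two-sided interval and in the planned anti-PRP GMCs.

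Two things remain. The null and alternative are the formal statement of the pre-specified claim, and both governing documents state it backwards. The protocol, moreover, contains no p1 - p2 definition, so there the direction rests on the aim sentence and Table 12.1 alone.

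**Conclusion.** The concern holds. The null and alternative of Hypothesis 14 contradict the hypothesis's own aim and every other statement of direction in the two documents. A transposition is by far the likeliest cause, because the stated 99.9% power is reproduced at 1b - 2b (99.93%) and not at 2b - 1b (99.35%).

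Under the plan's assumption of 95% in both subgroups the practical effect is under one percentage point in the chance of passing. It becomes decisive only if the true rates differ: at the illustrative 85% against 95%, the printed rule would almost surely accept a response that the intended rule accepts 2.8% of the time. The scope is one of 16 secondary hypotheses. The primary objectives, sample size and power are unaffected. It should be fixed, but it does not threaten the trial's main conclusions.

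**What to change.** Before database lock, print H0 as p(prp, G1b) - p(prp, G2b) ≤ -10% and H1 as p(prp, G1b) - p(prp, G2b) > -10% in SAP 5.1.2.1, protocol 12.1.2.1 and the protocol synopsis. Add a line to SAP 5.8 recording the correction.

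While there, tidy the group labels in SAP 5.1.2.2 to read Group 1 and Group 2, Subgroup 1a and 2a, or Subgroup 1b and 2b. In that sentence only the words Group and Subgroup are interchanged for the first two pairs; the arm order is already right.

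The cost is a few lines of text, with no new data, subjects or re-powering. Changing the protocol means a written amendment under protocol 5.4, with at least notification of the ethics committees. The SAP correction alone would settle the analysis, so it need not wait for the amendment.
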